## 8.8. Treatment Compliance

Compliance with study drug will be assessed over the Double-Blind Treatment Period and Run-In Period using drug dispensing records. Treatment compliance will be computed by determining the number of tablets taken relative to the number of tablets expected. Patients are expected to take two tablets per day, one from each of two bottles.

Treatment compliance based on the drug accountability will be calculated as follows:

- compliance (%) = (number of tablets taken)/(number of tablets expected)\*100
  - number of tablets taken = the number of tablets dispensed – the number of tablets returned
  - number of tablets expected = (date of the last dose - date of the first dose+1)

Summary of treatment compliance will be presented by treatment group, between Week 18 and 24 as well as overall. The number and percentage for compliance expressed as a categorical variable (<80%,  $\geq$ 80% to  $\leq$ 120%, and >120%) will be also presented by treatment group.

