IP for the Double-Blind Treatment Period (Weeks 0 to 24) will be supplied at Visits 3, 6, 8, 10, and 11. At each dispensing visit during the Treatment Period, subjects will be given an IP kit containing 2 bottles of IP. Depending on treatment assignment, subjects will receive either two bottles of 35 mg RVT-101 tablets, one bottle of 35 mg RVT-101 tablets and one bottle of placebo tablets, or two bottles of placebo tablets. Each bottle will contain 50 tablets, which is sufficient for 4 weeks plus 22 days overage (V3, V6, V8) and for 6 weeks plus 8 days overage (V10 and V12). Subjects will be instructed to take two tablets of IP daily at bedtime with or

without food; this will consist of one tablet from each of the two bottles in the kit. New bottles of IP will not be dispensed at Visits 4, 5, 7, and 9, however, drug accountability will be checked, and subjects will be re-dispensed the IP bottles they received at the previous dispensing visit. All subjects and their caregivers should be instructed to bring IP bottles, with any unused drug, to each visit. It is important that drug accountability is checked individually for each of the two dispensed bottles.

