- Completers (CS) Population: ITT subjects who have completed the Week 24 visit with non-missing endpoints for all three variables, the UPDRS-III, ADAS-Cog 11, and CIBIC+. This population will be used for supportive analysis of all efficacy variables except the UPDRS variables.
- UPDRS Completers Primary Analysis Population: UPDRS Primary Analysis Population Patients who have a Week 24 UPDRS Part III value. This will be run only on the UPDRS Part III and Part 5 variables.
- Pharmacokinetics (PK) Population: All subjects in the Safety Population who undergo plasma PK sampling and have at least one post-baseline evaluable PK concentration result.
- Per-Protocol (PP) Population: Subjects in the ITT Population who have no major protocol violations. The PP Population will not be analyzed if this population comprises more than 95% or less than 50% of the ITT Population. This population will be used for confirmatory analysis all efficacy variables except the UPDRS variables. The PP Population will be identified prior to breaking the study blind. Major protocol violations will be defined as follows:
  - Subject had >7 consecutive days interruption in double-blind study medication

- Treatment with excluded concomitant medications during the double-blind treatment period.
  - If taking an acetylcholinesterase inhibitor, subject had a change in AChEI dose or frequency during the double-blind treatment period.
  - Significant study drug administration errors.
  - Invalid baseline primary or secondary efficacy assessment.
  - Subject does not have MMSE score 14-26 inclusive at Screening and Baseline
  - Subject's baseline MMSE declined by 4 or more points from Visit 2 (Run-in) to Baseline
  - Evidence of other causes of dementia other than DLB as the primary cause
  - History or presence of significant medical or psychiatric condition at Screening.
  - Subject does not live with (or have substantial Periods of contact with) a regular caregiver [at least 10 hours total and at least 3 days per week]).
  - Subject is <80 % compliant or > 120% compliant between Visit 11 (Week 18) and Visit 12 (Week 24) with study drug. Patients who fail to return their bottle (and thus compliance cannot be determined) will be assumed to have been compliant for purposes of the Per Protocol population.

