## 9. EFFICACY

### 9.1. General Considerations

Tabulation of the primary and secondary endpoints will generally be presented for the ITT, Per-Protocol, and Completers Population. The primary and secondary endpoints will be tabulated for the subgroups, while other variables may be added for subgroup analysis. Efficacy assessments will be performed on the observed cases dataset unless otherwise specified. The UPDRS Primary Analysis Population will form the basis for the primary conclusions regarding the primary efficacy variable (for the UPDRS Part III), while the ITT Population will form the basis for conclusions regarding all other endpoints. The UPDRS Part 5 will also be assessed using the UPDRS Primary Analysis Population.

Baseline or pre-dose assessment is the last available non-missing assessment prior to time of first dose of double-blind treatment, unless otherwise specified. If there are multiple efficacy assessments for a given parameter collected on the same date, the later of these assessments will be used.

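### The SAP 8.8 compliance formula omits the factor of 2 for two tablets a day, so as written scores are doubled and adherent patients become Per-Protocol violators

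*SAP*

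**What the plan says.** SAP 8.8 (Treatment Compliance) describes the regimen as follows: "Patients are expected to take two tablets per day, one from each of two bottles". Compliance is 100 x tablets taken / tablets expected. Tablets taken is the number dispensed minus the number returned, with no restriction to one bottle. The denominator is "number of tablets expected = (date of the last dose - date of the first dose+1", which is a number of days. The result is tabulated for Weeks 18 to 24 and overall, in the categories below 80%, 80% to 120% and above 120%.

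SAP 7.4 uses the score to define populations. For both the PP and the UPDRS PP populations, one major violation is: "Subject is <80 % compliant or > 120% compliant between Visit 11 (Week 18) and Visit 12 (Week 24) with study drug". It adds: "Patients who fail to return their bottle (and thus compliance cannot be determined) will be assumed to have been compliant". It also sets a size rule: "The PP Population will not be analyzed if this population comprises more than 95% or less than 50% of the ITT Population".

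Protocol 7.1 supplies two bottles per kit at each dispensing visit. For the four-week intervals it says "Each bottle will contain 50 tablets, which is sufficient for 4 weeks plus 22 days overage", and for the six-week intervals the same 50 tablets are said to cover 6 weeks plus 8 days. On pill counts it says: "It is important that drug accountability is checked individually for each of the two dispensed bottles".

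**The concern.** The numerator counts tablets from both bottles, two a day. The denominator counts one a day. The ratio is therefore twice the true adherence, yet it is compared with limits that only make sense on the true scale.

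Three outputs depend on it:

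- **PP and UPDRS PP membership.** Patients who took their tablets and returned their bottles are excluded for scoring above 120%. Those kept are non-returners, who are deemed compliant, and patients who took roughly half their tablets, unless another violation rule removes them. That reverses the purpose of a per-protocol set. The UPDRS PP population is meant to confirm the primary endpoint.
- **Whether the PP analyses are run at all.** If enough adherent patients are excluded, the population falls below half of ITT and the SAP's own rule cancels the analysis.
- **The compliance table**, which would show fully adherent patients in the highest category.

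**Working it through.** **Inputs.** Two tablets a day (SAP 8.8; Protocol 7.1). Two bottles of 50 tablets per kit (Protocol 7.1). Week 18 is Day 126 and Week 24 is Day 168 (schedule of events), so the interval is 168 - 126 = 42 days. The protocol's list of dispensing visits puts the last kit at Visit 11; its supply sentence says Visit 12, and I use Visit 11.

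**Supply check.** The plan gives no compliance value to reproduce, but its supply figures can be checked at one tablet per bottle per day: run-in 14 + 36 = 50; four-week interval 28 + 22 = 50; six-week interval 42 + 8 = 50. All agree with 50 per bottle, hence 2 x 50 = 100 per kit, and confirm two tablets a day.

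**Fully adherent patient, Weeks 18 to 24, with the dates of that interval.** Dispensed 100; taken 2 x 42 = 84; returned 100 - 84 = 16.

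- As written: (100 - 16)/42 = 84/42 = 200%.
- With the factor of 2: 84/(2 x 42) = 84/84 = 100%.

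The doubling does not depend on interval length: run-in 28/14 = 200%; the whole 24 weeks 336/168 = 200%.

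**Who passes the 80-120% rule as written.** 0.80 x 42 = 33.6 and 1.20 x 42 = 50.4, so 34 to 50 tablets pass.

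| Tablets taken of 84 | True adherence | Score as written |
|---|---|---|
| 84 | 100% | 200% |
| 51 | 60.7% | 121.4% (violation) |
| 50 | 59.5% | 119.0% |
| 42 | 50% | 100% |
| 34 | 40.5% | 81.0% |

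**Alternative readings.**

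- *Per bottle:* (50 - 8)/42 = 42/42 = 100%. The denominator is then right, but the result is one score per bottle.
- *Whole-period dates with only the Visit 11 kit:* SAP 8.8 does not say which first and last dose dates apply to the Week 18-24 score. With first and last dose of the whole treatment period, the adherent patient scores 84/168 = 50%. That is below 80% rather than above 120%, and still a violation.

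**Could PP fall below 50% of ITT?** The documents do not give the needed rates, so this is an assumption. Let w be the share of ITT kept in without a computable score, and a the share of the rest with true adherence above 60%. With no other violations,

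PP/ITT is at most w + (1 - w)(1 - a) = 1 - a(1 - w).

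This is below 0.5 when w < 1 - 0.5/a:

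- a = 0.80: w below 37.5%
- a = 0.90: w below 44.4%
- a = 0.95: w below 47.4%

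The UPDRS PP population has the same violation list, is drawn from a subset of ITT and is measured against the same ITT denominator, so its share cannot be larger.

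**The case against.** The strongest reply is that the formula is meant per bottle. Protocol 7.1 and 7.6 require accountability for each bottle, the non-return rule in SAP 7.4 speaks of a bottle in the singular, and one bottle gives exactly 42/42. This is a fair reading of intent. However, those protocol sections govern pill counts at the site. The SAP states no per-bottle calculation and gives no rule for turning two bottle results into the single figure that the PP rule tests. SAP 7.3 also gives the SAP precedence over the protocol on analysis. If per bottle was meant, the text still needs correcting.

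Second, the two-tablet regimen is stated just above the formula, scores near 200% would be conspicuous, and the PP list is fixed before unblinding. A programmer may well catch the error. That makes it easy to correct, but a rule that defines a population should not rely on an informal repair.

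Third, the 200% for the PP rule assumes interval dates. That stands: with whole-period dates the adherent patient scores 50% instead. The direction of the error changes, but the patient is still misclassified.

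Fourth, not every patient at half adherence stays in. Interruptions of more than 7 consecutive days and significant administration errors are separate violations. This also stands, and limits that consequence to patients who escape those rules.

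Finally, the impact is bounded. SAP 9.1 says "The UPDRS Primary Analysis Population will form the basis for the primary conclusions regarding the primary efficacy variable", and the ITT population supports the other endpoints. Neither uses the compliance score.

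**Conclusion.** The formula is wrong as written and nothing elsewhere in the SAP corrects it. On the pooled reading, with interval dates, every score is exactly twice the true value and the 80-120% band selects 40.5% to 59.5% true adherence over Weeks 18 to 24. The compliance table and both per-protocol populations would be wrong.

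The doubling rests only on the documents' own figures. Whether PP would drop below 50% of ITT rests on the assumed values of a and w; it is a possibility, not a forecast.

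This should be fixed, but it is not critical: the primary UPDRS-III analysis, the ITT analyses and the safety populations are untouched.

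**What to change.** In SAP 8.8, define tablets expected = 2 x (last dose date - first dose date + 1), and state that the dates are those of the interval assessed; for the PP rule, Visit 11 to Visit 12. Both parts are needed, since the factor of 2 alone does not settle which dates apply.

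If a per-bottle calculation was intended, say so instead, and state how the two bottle results are combined into one figure.

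The 80-120% limits can stay: with the factor restored they again refer to the prescribed number of tablets. The cost is one line of SAP wording and the matching line of code, made while blinded and before the PP exclusion list is final. No new data are needed.

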## 8.9. Overdose

A listing of any overdose information will be provided. This will be included in the same section of the data listings as the compliance listings. Any dose of intepirdine greater than 105 mg within a 24-hour time period will be considered an overdose. Cases of overdose were to be documented in the CRF. Overdose in the absence of other AEs were not be reported as an AE in its own right.

## 9. EFFICACY

### 9.1. General Considerations

Tabulation of the primary and secondary endpoints will generally be presented for the ITT, Per-Protocol, and Completers Population. The primary and secondary endpoints will be tabulated for the subgroups, while other variables may be added for subgroup analysis. Efficacy assessments will be performed on the observed cases dataset unless otherwise specified. The UPDRS Primary Analysis Population will form the basis for the primary conclusions regarding the primary efficacy variable (for the UPDRS Part III), while the ITT Population will form the basis for conclusions regarding all other endpoints. The UPDRS Part 5 will also be assessed using the UPDRS Primary Analysis Population.

Baseline or pre-dose assessment is the last available non-missing assessment prior to time of first dose of double-blind treatment, unless otherwise specified. If there are multiple efficacy assessments for a given parameter collected on the same date, the later of these assessments will be used.

### 9.2. Statement of the Null and Alternate Hypothesis

This study will examine the following primary hypothesis:

- $H_0$ : There is ***NO*** difference between treatment with intepirdine and treatment with placebo with respect to changes over 24 weeks in the UPDRS-III score in patients with DLB disease.
- $H_a$ : There ***IS*** a difference between treatment with intepirdine and treatment with placebo with respect to changes over 24 weeks in the UPDRS-III score in patients with DLB disease.

The primary comparisons of interest will be performed at the 5% level of significance. All hypothesis tests will be two-sided.

### 9.3. Analysis of the Primary Efficacy Endpoint

The primary efficacy endpoint is the change from Baseline in the UPDRS-III total score at Week 24. The primary method of analysis will be using a mixed model for repeated measures (MMRM), with supportive method being the Wilcoxon rank statistic (a nonparametric test).

For the primary efficacy and secondary efficacy variables ONLY, in addition to the primary pairwise analyses, a table will be presented that will compare the POOLED data (pooled across the 35 mg and 70 mg Intepirdine arms) vs placebo. This will be done ONLY for the MMRM analysis.

#### 9.3.1. MMRM

Primary treatment comparisons between Intepirdine and placebo will be performed on the change from Baseline to Week 24 using an MMRM with restricted maximum likelihood estimation, an unstructured covariance matrix, and the Kenward-Roger approximation for denominator degrees of freedom. The model will include terms for treatment, visit, treatment by

visit interaction, pooled geographic region, baseline MMSE score, the baseline value, and the baseline value by visit interaction.

- The region by treatment interaction term will be evaluated at the 10% level of significance; if the interaction term is found to be significant, it will be included in the MMRM model. Note, this applies to ALL MMRM models.
  - For the by-region Subgroup analyses, where, because the subgroup analyses by Region only include 1 region, the interaction makes no sense. The same MMRM model is also used for subgroups for the primary efficacy endpoint, as appropriate.

As additional supportive information, treatment differences at *each post baseline visit* will also be derived using the MMRM model; however, primary inferences will be drawn from treatment differences derived from the MMRM models at Week 24.

The estimated treatment difference (“Intepirdine 35mg – Placebo” and “Intepirdine 70mg – Placebo”) at each visit will be displayed in the summary of statistical analysis together with the 95% confidence interval and the associated p-value.

No imputation of the missing values will be performed for the primary analyses, ie, the data used in the analysis will be the actual observed responses at each visit.

Least Squares Means for each visit will also be presented with the standard error and the number of subjects contributing to the Least Squares Means. Least Squares Means and estimated treatment differences for each visit and the associated 95% confidence interval will be displayed graphically.

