	
secondary endpoint, in order to maintain an overall 5% significance level within that dose.
 
Sample Size:
 
The sample size is based on assumptions of treatment benefit for one primary endpoint, the UPDRS- III total score. A sample size of 70 subjects per treatment group will allow a treatment difference of 4 points between placebo and active treatment in the change from baseline in UPDRS- III score to be detected with 88% power and a 0.05 significance level assuming an underlying standard deviation (SD) of 7.5
 
There are two secondary endpoints:
 

• ADAS-Cog 11 total score. A sample size of 80 subjects per treatment group will allow a treatment difference of 3 points between placebo and active treatment in the change from baseline in ADAS-Cog-11 score to be detected with 88% power and a 0.05 significance level assuming an underlying standard deviation (SD) of 6. Under the assumptions of a 2.5, 2.0 and 1.5 point treatment effect, the power is 74%, 55% and 35%, respectively.

• CIBIC+. A sample size of 80 subjects per treatment group will allow a treatment difference of 0.5 points between placebo and active treatment in the observed values in the CIBIC+ to be detected with 91% power and a 0.05 significance level assuming an underlying standard deviation (SD) of 0.95. Under the assumptions of a 0.4 and 0.3 point treatment effect, the power is 75% and 51%, respectively.

 
Randomization will be stratified according to Baseline MMSE score in the groupings of 14-17 points, 18-21 points and 22-26 points and according to whether subjects are or are not taking a cholinesterase inhibitor as a concomitant medication.
 
Efficacy:
 
The primary efficacy endpoint is the change from Baseline in the UPDRS-III total score at Week 24. Primary treatment comparisons between Intepirdine and placebo will be performed on the change from Baseline to Week 24 using an MMRM with restricted maximum likelihood estimation, an unstructured covariance matrix, and the Kenward-Roger approximation for denominator degrees of freedom. The model will include terms for treatment, visit, treatment by visit interaction, pooled geographic region, baseline MMSE score, and use of cholinesterase inhibitor at baseline (Yes/No) as covariates.

--	---

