## 7.2. Randomization/Treatment Assignment

Subjects will be assigned to receive 35 mg RVT-101, 70 mg RVT-101, or placebo in accordance with the randomization schedule, prior to the start of the Double-Blind Treatment Period, using validated software.

Following confirmation of eligibility at the end of Single-Blind Run-In Period, subjects will be randomized to placebo or 35 mg RVT-101, 70 mg RVT-101 in a 1:1:1 ratio. Randomization will be stratified according to Baseline MMSE score in the groupings of 14-17 points, 18-21 points and 22-26 points and according to whether subjects are or are not taking a cholinesterase inhibitor as a concomitant medication.

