### **10.4.1. Primary Efficacy Analyses**

The primary efficacy endpoint is the change from Baseline in the UPDRS-III total score at Week 24. The primary method of analysis will be using a mixed model for repeated measures (MMRM), with supportive method being the Wilcoxon rank statistic (a nonparametric test).

For the primary efficacy and secondary efficacy variable ONLY, in addition to the primary pairwise analyses, a table will be presented that will compare the POOLED data (pooled across the 35 mg and 70 mg Intepirdine arms) vs placebo. This will be done ONLY for the MMRM analysis.

Primary treatment comparisons between Intepirdine and placebo will be performed on the change from Baseline to Week 24 using an MMRM with restricted maximum likelihood estimation, an unstructured covariance matrix, and the Kenward-Roger approximation for denominator degrees of freedom. The model will include terms for treatment, visit, treatment by visit interaction, pooled geographic region, baseline MMSE score, the baseline value, and the baseline value by visit interaction.

As additional supportive information, treatment differences at each post baseline visit will also be derived using the MMRM model; however, primary inferences will be drawn from treatment differences derived from the MMRM models at Week 24.

The estimated treatment difference (“Intepirdine 35mg – Placebo” and “Intepirdine 70mg – Placebo”) at each visit will be displayed in the summary of statistical analysis together with the 95% confidence interval and the associated p-value.

No imputation of the missing values will be performed for the primary analyses, ie, the data used in the analysis will be the actual observed responses at each visit.

Least Squares Means for each visit will also be presented with the standard error and the number of subjects contributing to the Least Squares Means. Least Squares Means and estimated treatment differences for each visit and the associated 95% confidence interval will be displayed graphically.

The nature of missing data will be explored and the extent of missing data pattern will be summarized. Details will be provided in the SAP.

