### 7.3. General Table and Individual Subject Data Listing Considerations

Tables, listings and figures will be prepared in accordance with the current International Conference on Harmonization Guidelines. The information and explanatory notes in the “footer” or bottom of each table and listing will include the following information:

- Date of output generation
- SAS® program name, including the path that generates the output
- Any other output specific details that require further elaboration

All hypothesis tests and confidence intervals will be two-sided at an alpha level of 5%.

Version 9.1 or higher of the SAS system will be used to analyze the data as well as to generate tables, figures, and listings.

In general, tables will be formatted with a column displaying findings for all subjects combined. The summary tables will clearly indicate the number of subjects to which the data apply, and “unknown” or “not performed” will be distinguished from “missing” values data.

The treatment groups will be referred to in the tables, listings, and figures with the following conventions (and in this order, left to right, in the tables):

- Placebo
- Intepirdine 35 mg
- Intepirdine 70 mg
- Total (all 3 treatment groups combined)

For the primary efficacy and secondary efficacy variables ONLY, a table will be presented that will compare the POOLED data (pooled across the 35 mg and 70 mg Intepirdine arms) vs placebo.

Data analyses will be performed by, or under the direct supervision of, Axovant Sciences. Listings will be sorted by subject, period and time, or as appropriate. Tabulations will be presented by treatment and time. Unless stated otherwise, descriptive summaries will include n, mean, standard deviation, median, minimum, and maximum for continuous variables, and n and percent for categorical variables.

The geometric mean with associated 95% CI, between-subject CVs (CVb), and SD of the logs based on the geometric mean, will be included for the log-transformed PK parameters. The between-subject %CV of the log transformed variable will be calculated as:

- $\%CVb = 100 * \sqrt{(e^{SD^2} - 1)}$ , with SD of the log-transformed data

Deviations from the analyses as described in this SAP will be identified in the final Clinical Study Report. When differences exist between the protocol-described analysis and the SAP, the SAP will take precedence.

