#### **9.3.1.1. Further Details of the MMRM Analysis**

The mixed model for repeated measures (MMRM) model will be fitted using SAS PROC MIXED procedure with restricted maximum likelihood estimation, an unstructured covariance matrix, and the Kenward-Roger approximation for denominator degrees of freedom. The unstructured covariance is the least restrictive and generally performs well with limited number of repeated measures per patient and puts no parameters on the data with respect to the covariance structure assumptions.

- Only in the unlikely circumstance that there are convergence problems with the MMRM analysis will other covariance structures be examined to resolve the convergence issue, ie, we would evaluate other additional variance-covariance structures, including compound symmetry (CS), heterogeneous compound symmetry (CSH), and auto-regressive [AR(1)]. In this eventuality, the Akaike’s Information Criterion (AIC) will be used to determine the optimal variance-covariance structure matrix for the primary comparisons.
  - If convergence issues arise, the base by visit interaction may be dropped.

*Sample* SAS code is as follows. The actual SAS code may be modified as appropriate. Note that the treat\*region interaction will be assessed for significance (at alpha 0.10), and if not significant, will be dropped from the model.

```
ods trace on;
```

```
Proc mixed data=MMRM1 method=reml PLOTS (MAXPOINTS=200000000000);
  class usubjid trt avisitn region;
  model chg=trt avisitn trt*avisitn trt*region base basemmsescore
base*avisitn region /ddfm=kr;
  repeated avisitn/subject=usubjid type=un r;
  lsmeans trt*avisitn/pdiff cl ;
  lsmeans trt*region/pdiff alpha =0.10;
  ods output lsmeans=_LS diffs=_lsdiff tests3 =tst;
run;
ods trace off;
```

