#### 9.3.4.2. Last Observation Carried Forward

An ANCOVA model will be run on the Week 24 data for which any missing values at Week 24 are imputed from last non-missing value carried forward (LOCF) for a given patient. If there are no on-treatment values for a patient, the baseline (last pre-treatment) observation will be carried forward.

*Sample* SAS code is as follows (where bascore is the baseline score for the endpoint and center is the pooled geographic region variable.

```
Proc Mixed data=dat;  
  Class treat MMSEbase center;  
  Model outcome=treat mmsebase center bascore;  
  Run;
```

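### The primary MMRM omits cholinesterase-inhibitor use, a randomisation stratum, and a 10% pre-test decides whether treatment-by-region enters the model

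*SAP*

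**What the plan says.** **Stratification.** Protocol 7.2 stratifies randomisation by three MMSE bands and "according to whether subjects are or are not taking a cholinesterase inhibitor as a concomitant medication". SAP section 6 repeats this.

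**Primary model.** The documents give two covariate lists:
- The protocol synopsis includes "baseline MMSE score, and use of cholinesterase inhibitor at baseline (Yes/No) as covariates". It does not list baseline UPDRS-III or its interaction with visit.
- Protocol 10.4.1 lists "pooled geographic region, baseline MMSE score, the baseline value, and the baseline value by visit interaction". SAP 9.3.1 has the same covariates ("visit interaction, pooled geographic region, baseline MMSE score, the baseline value, and the baseline value by visit interaction"), and so does the sample code in 9.3.1.1. None of the three has inhibitor use.

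SAP 7.3 settles which text governs: "When differences exist between the protocol-described analysis and the SAP, the SAP will take precedence". The operative model therefore has no inhibitor term.

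**Other analyses.** The LOCF model in SAP 9.3.4.2 is "Model outcome=treat mmsebase center bascore". The multiple-imputation analysis (9.3.4.3), the general ANCOVA (9.4) and the sample CMH code for a tertiary endpoint (9.4.2) also omit inhibitor use. The falls CMH in SAP 10.1 uses both strata.

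**Region.** SAP 9.3.1 tests region-by-treatment at 10% in every MMRM, and "if the interaction term is found to be significant, it will be included in the MMRM model". Section 9.3.1.1 says the term "will be assessed for significance (at alpha 0.10), and if not significant, will be dropped from the model". Neither the synopsis nor protocol 10.4.1 contains this step.

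**The concern.** **Omitted stratum.** Stratified randomisation makes the arms alike on inhibitor use, so the treatment estimate already has the smaller variance that this balance brings. A model without the factor leaves the factor's variation in the residual and reports a larger standard error than the estimate really has. The intervals are then too wide and some power is given up. This happens only if inhibitor use predicts 24-week UPDRS-III change beyond baseline score, MMSE and region.

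**Pre-test.** With treatment-by-region out of the model, the Week 24 contrast weights regions roughly by patients. With the term in, the default LSMEANS of the sample code give each region equal weight. As an illustration, take regional shares of 70/20/10 and true effects of 5, 2 and 1 points. The patient-weighted effect is 0.7×5 + 0.2×2 + 0.1×1 = 4.0, and the equally weighted effect is (5+2+1)/3 = 2.7. A preliminary test on the same data decides which of these the primary analysis estimates.

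The first issue makes the test conservative and the second makes it slightly liberal, so they do not share a justification. Both act on the 70 mg primary comparison, which under SAP 7.5 gates the 35 mg test and the secondary endpoints.

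**Working it through.** **1. The plan's own figure.** Inputs from SAP section 6: 70 per arm, difference 4, SD 7.5, two-sided 5%.
- Standard error = 7.5 × √(2/70) = 1.268.
- Noncentrality = 4/1.268 = (4/7.5) × √35 = 3.155.
- Power is 88.4% (normal) or 88.0% (t), so the stated 88% reproduces.

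**2. Omitted stratum.** Let R² be the share of residual variance that inhibitor use explains; the documents give no value. Take 7.5 as the residual SD of the model without the term, and assume near-exact balance.
- True SD of the estimate = √(1−R²) × model standard error.
- Overstatement = 1/√(1−R²) − 1.
- Type I error = 2 × [1 − Φ(1.96/√(1−R²))].
- Power comes from the noncentral t with 200 df, with noncentrality 3.155/√(1−R²). The critical value is divided by √(1−R²) when the term is omitted.
- Difference between users and non-users that this R² implies, at an assumed 60% users: b = 7.5 × √(R²/(0.6×0.4)).

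| R² | b (points) | SE overstated | Type I error, omitted | Power omitted → included | Gain (points) |
|---|---|---|---|---|---|
| 0 | 0 | 0 | 5.0% | 88.1 → 88.1% | 0 |
| 1% | 1.5 | 0.5% | 4.9% | 88.2 → 88.4% | 0.2 |
| 2% | 2.2 | 1.0% | 4.8% | 88.3 → 88.7% | 0.4 |
| 5% | 3.4 | 2.6% | 4.4% | 88.7 → 89.6% | 1.0 |
| 10% | 4.8 | 5.4% | 3.9% | 89.3 → 91.2% | 1.8 |

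Gains are taken before rounding. A simulation agrees (30,000 trials per setting, permuted blocks within the six strata, two-visit REML MMRM). Power goes from 88.0 to 88.4% at R² 2%, from 88.3 to 89.3% at 5%, and from 88.9 to 90.7% at 10%.

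**3. Pre-test.** Each setting has 40,000 simulated three-arm trials with 70 per arm, three regions, complete data and no true interaction. The model is a REML MMRM with unstructured covariance, with the terms of the sample code. Treatment-by-region is tested on 4 df at 10%; if kept, regions get equal weight. Visits are Weeks 4 and 24 (as in SAP 9.3.2) or Weeks 1, 4 and 24. The assumptions are:
- regional shares and the number of regions;
- change SDs of 5.0 and 6.0 at the earlier visits (7.5 at Week 24 is the plan's);
- between-visit correlations of 0.3 to 0.7 (0.3 and 0.7 run only for the two most unequal splits);
- residual df in place of Kenward-Roger.

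The term is kept in 10–11% of trials. Results for the whole procedure:

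| Regional shares | Type I error, pre-test | Type I error, fixed model | Power lost (points) |
|---|---|---|---|
| Equal | 4.9–5.0% | 4.9–5.0% | none |
| 50/25/25 | 5.1% | 4.9–5.0% | 0.3 |
| 60/25/15 | 5.4–5.5% | 5.1–5.2% | 0.9–1.2 |
| 70/20/10 | 5.4–5.8% | 5.0–5.1% | 1.7–2.5 |

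At 70/20/10, power is 85.3–86.2% against 87.6–88.1%. Simulation error is about 0.1 point for type I error and 0.2 for power.

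A separate single-visit simulation gives similar or slightly larger effects. Type I error is 5.5% against 4.9% at 60/25/15, and 5.8% against 4.9% at 70/20/10. Power is 85.4% against 87.1%, and 84.7% against 87.5%. Among trials that keep the term, type I error is 10.4% and 13.1%.

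**The case against.** The case against is mainly about size, and much of it stands.
- **The stratum effect is conservative and conditional.** It cannot raise type I error, and the documents give no evidence that inhibitor use is prognostic for motor change. At 60% users, the 10% row needs a 4.8-point difference between users and non-users, more than the 4-point drug effect assumed. At 1–2% the gain is only 0.2–0.4 power points.
- **Balance is only approximate in the analysis set.** The UPDRS Primary Analysis Population (SAP 7.4) excludes patients on post-randomisation score and medication changes, so the conservative type I errors above are approximations. This is not a reason to leave the factor out.
- **The larger pre-test figures need marked regional imbalance.** Three regions come from the subgroup list in SAP 7.8, and the plan does not say that these are the model's pooled regions. A single-visit check with two regions at 60/40 gives 5.1% against 5.0% and 0.3 power points lost. Three regions at 40/35/25 give 5.2% for both and 0.2 points lost. At 60/25/15 the fixed model itself runs at 5.1–5.2%, so the net rise is about 0.3 points.
- **Equal weighting comes from sample code** that the SAP says may be modified. The SAP text sets no other weights, so this is the only reading on offer.
- **Inhibitor use is already a planned subgroup** (SAP 7.8). That describes effects by user status; it does not correct the primary standard error.

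The pre-test rule is itself pre-specified, so it is not a post hoc choice. The model it yields still depends on the data.

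**Conclusion.** The concern holds on both counts, and both effects are small. The governing model leaves out a factor used in randomisation, without a stated reason and against the synopsis. The cost is nil if the factor is not prognostic. If it explains 1–10% of residual variance, the standard error is overstated by 0.5–5.4% and 0.2–1.8 power points are given up. The pre-test makes the primary model and its regional weighting depend on the data. The cost is nil with equal regions and rises to about 0.4–0.7 points of type I error and 1.7–2.5 points of power at 70/20/10. The R², the share of inhibitor users, the regional shares and the number of regions are not in the documents, so these are ranges and not predictions. The case for change is that both effects sit on the gating primary test, the protocol's two model descriptions must be reconciled in any event, and the correction is nearly free while the trial is blinded.

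**What to change.** 1. Add baseline cholinesterase-inhibitor use (yes/no) to the efficacy MMRM and ANCOVA models, including the LOCF and multiple-imputation analyses, and to the strata of the efficacy CMH tests.
2. Fix the primary MMRM without treatment-by-region. Report the interaction test and the by-region estimates already planned in SAP 7.8 as exploratory.
3. Make the protocol synopsis, protocol 10.4.1 and SAP 9.3.1 and 9.3.1.1 state one model. Keep the baseline UPDRS-III and baseline-by-visit terms, which the synopsis lacks.

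The cost is wording in the SAP, the synopsis and protocol 10.4.1, one variable already collected for randomisation, and one degree of freedom. It needs to be done before unblinding, because a later change of model would look driven by the result.
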